### ***Metabolic Syndrome Markers and Anabolic Hormones***

A fasting approximately 20ml blood sample will be collected for assessment of lipids and HbA1c. Samples will also be stored at -80C for later measurement of IGF1 and IGFBP1 and other markers.

### ***Body composition (DXA scan)***

Dual Emission X-Ray Absorptiometry uses a very low dose of radiation. This scanning machine provides a measure of body composition that is practical within a clinical setting. (Protocol can be found in **Appendix G**). These scans will be performed at 0, 3 and 12 months time points at the Charles Perkins Centre by a trained technician.

### ***Bioimpedance Spectroscopy (4 compartment model)***

Bioimpedance spectroscopy will be performed at 0, 3 and 12 months time points. (Protocol can be found in **Appendix I**)

### ***Questionnaires***

The following questionnaires will be completed at 0, 3 and 12 months:

1. The Epworth Sleepiness Scale (ESS)
2. Functional Outcomes of Sleep Questionnaire (FOSQ)
3. Depression, Anxiety and Stress Scales (DASS)
4. Impact of Weight on Quality of Life questionnaire (IWQOL)
5. International Physical Activity Questionnaire (IPAQ)

All questionnaires can be found in Appendix E

### ***Weight Loss and Maintenance***

Weight loss and maintenance education will be provided by the study dietitian/nutritionist to all patients during the three month randomised controlled phase at the 0, 1, 2 and 3 month visits and the 1w and 2w phone or video conference consultations. The focus during this period is complying with the VLED.

After the three month randomised controlled phase all patients will be offered continued weight maintenance from the study dietitian/nutritionist for the nine month follow up phase. The frequency of the follow up visits is at the discretion of the patient. The recommended schedule of clinic visits is at 9 and 12 months and

telephone or video conferencing consultations at 5 and 7 months, which is based upon a previously published Woolcock Institute clinical trial. The weight maintenance program consists of a manualised dietary and exercise component, aiming to maintain a minimum 10% weight loss over a 12 month period with sustainable changes in eating patterns and prescribed physical activity.

### ***Dietary Component***

All participants will undergo a VLED in the first 2 months to enable rapid weight loss of approximately 10% body weight. The VLED will be followed by a transitional period of 4 weeks into a low GI/high protein weight maintenance diet. During the maintenance diet, total daily energy intake is prescribed according to a participants' energy requirements, estimated using the Harris-Benedict equation with an appropriate activity factor and 2000 kJ (500 calorie) per day deficit to encourage moderate weight loss (approximately 0.5 kg per week) among participants. Dietary compliance will be monitored with a 4-day food diary administered at 0, 3 and 12 months.

### ***Exercise Component***

The exercise component aims to encourage patients to achieve greater than 250 minutes of exercise a week which is conducive to clinically significant weight loss and metabolic improvements. In addition, they will be prescribed a minimum 2 days per week self-managed strength training to promote lean muscle gain. Physical activity will be assessed at 0, 3 and 12 months using the International Physical Activity Questionnaire (IPAQ). In addition, all subjects will be issued with a wrist accelerometer to objectively measure but also potentially enhance physical activity. Activity data from these devices will be available online to investigators.

### ***OSA and CPAP Management***

Team sleep clinicians and CPAP therapists will manage OSA and CPAP therapy according to standard clinical practice. Patients will use auto-titrating CPAP during the randomised controlled phase of the trial. After the 3 month followup visit, all patients who commence or continue with CPAP therapy may use either auto-CPAP or fixed CPAP as deemed appropriate by the treating sleep physician. Clinic CPAP

therapists will download compliance data at 2 weeks, 3 months and as clinically indicated.

### ***Diaries***

Patients will be asked to document diet, exercise, and sleep habits daily at periods during the trial. They will also be asked to complete a 4-day food diary at 0 months, 3 months, 9 months and 1 year. 24-hr food recall will also be undertaken at 0 weeks, 2 months, 3 months, 5 months and 7 months to confirm dietary compliance. See Appendix F.

### ***Overnight Sleep Studies: Polysomnography (PSG)***

At three points during the study (screening, 3 and 12 months[if clinically indicated]) patients will undertake overnight polysomnography at the Woolcock Institute for the purpose of determining sleep apnoea severity measured primarily via the apnoea hypopnea index (AHI). This requires the attachment of leads to the patient in order to measure chest and abdominal movement, airflow at the mouth and lips, blood oxygen level, muscle tone, eye movements, heart rate and electrical activity in the brain. The study is scored using standard criteria.

## **3.9 Adverse Event Reporting**

Collection of adverse events will commence from the time that the participant signs the consent to participate in the study. Routine collection of adverse events will continue until the participant completes the study or withdraws.

Adverse events are defined as any untoward medical occurrence in a patient that occurs during the trial, which does not necessarily have a causal relationship with the interventions.

If the investigator believes that the adverse event is causally related to the VLED or CPAP device then adjustment or ceasing the use of the diet or device should be considered. This will be assessed by the investigators, study doctors and other members of the study team.

Serious adverse events (SAE's) are defined as any untoward medical occurrence that:

- Results in death
- Is an immediately life-threatening condition
- Requires hospitalisation or prolongs hospitalisation
- Results in persistent or significant disability/incapacity
- Is a congenital anomaly/birth defect
- Results in any other important medical condition.

The Ethics Committee must be notified of any SAE's within 72hours.

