## ***2.3 Participant Withdrawal***

### ***Withdrawal criteria***

Participants will be informed that they have the right to withdraw from the study at any time without prejudice to their medical care, and are not obliged to state their reasons. The investigator will follow up any withdrawals.

Additionally, the investigator may withdraw a patient at any time for the following reasons:

1. If any of the study exclusion criteria are diagnosed
2. Protocol violations
3. Adverse or serious adverse events

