### ***Procedure to withdraw***

If a participant fails to return for follow up or discontinues for personal reasons, attempts will be made to determine whether the reason for not returning is not an adverse event (bearing in mind that the participant is not obliged to state his/her reasons).

Participants with clinically significant abnormalities requiring discontinuation will be followed until recovery from the abnormality, if possible.

For the reasons above, if discontinuation occurs, an early termination visit will be encouraged with an attempt to collect the primary outcome.

If the study is discontinued for safety reasons, the investigators must contact all affected participants within a reasonable time frame to inform them of the termination of their involvement in the study.

Participants discontinuing from the study may be replaced. A new randomisation number must be issued for the new participant.

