### ***3.5 Risks and Discomforts***

VLED: Minor side effects such as fatigue, constipation, diarrhoea, nausea, dizziness, headache, irritability and cold intolerance are usually transient and rarely prevent patients from completing the VLED program. Longer term side effects such as dry skin, hair loss and brittle nails usually subside with the re-introduction of a standard weight maintenance diet. In extreme cases vomiting, acute gout, acute gall bladder disease or cardiac disturbances (particularly if electrolyte disturbances) may preclude therapy.

[figure not shown]
Blood Test: There may be some discomfort from the venepuncture and cannular insertion at the site from which blood is taken. There is also a risk of some minor bruising at the site, which may last one to two days.

DXA Scans: This research study involves exposure to a very small amount of radiation. The dose from routine diagnostic X-ray and nuclear medicine procedures is 2 mSv to 20 mSv. The effective radiation dose from this study is about 0.54 mSv. At this dose level, no harmful effects of radiation have been demonstrated and the risk is very low.

In addition to the risks or discomforts listed here, there may be other known and unknown risks that are not disclosed here; patients should talk to the study doctor if they would like more information.

In addition, patients may have a right to take legal action to obtain compensation for any injuries or complications resulting from the study. Compensation may be available if their injury or complication is sufficiently serious and is caused by unsafe drugs or equipment, or by the negligence of one of the parties involved in the study (for example, the researcher, the hospital, or the treating doctor). Patients do not give up any legal rights to compensation by participating in this study.

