##### ***Data Analysis:***

Outcome data will be analysed using Linear Mixed Model Analysis of variance due to expected inter-patient variability and repeated measures. Patients will be random

factors. Treatment and time (0 & 3 months) will be fixed factors. The Treatment x Time interaction will be examined to see the specific difference between treatments at just the 3 month time point. Analysis will be by intention to treat and will include all participants who are randomised at 0 months including drop-ins to CPAP and participants who do not adhere to treatment.

Exploratory mixed models analyses of OSA severity accounting for CPAP compliance and weight change will also be conducted using 12 month followup data.

**Data Monitoring:** As all treatments are routinely applied in clinical care, a Data Monitoring Committee will not be appointed. Instead, all adverse events and serious adverse events will be monitored by the investigating team and discussed at regular monthly meetings. Patients who develop excessive sleepiness in the weight loss alone arm will be assessed by the study sleep physicians to determine the cause of the sleepiness and be considered on a case-by-case basis for being placed on CPAP therapy. Side effects attributable to the VLED will be managed by the dietician in consultation with the endocrinology/metabolic physician team.

There are no planned interim analyses. The final decision to terminate the trial lies with the Principal Investigators. Stopping guidelines will be based on (1) safety data and (2) ongoing trial funding. The investigators will conduct a 6 monthly review of all SAEs (pre-defined on page 22) and if after discussion the rate of SAE's is deemed unacceptable by the PI's then the study will be stopped and the HREC will be advised of the decision.

Internal procedures for monitoring trial conduct will be followed. Where available an external monitor will be engaged.

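### Routine adverse event collection ends at withdrawal, which the investigator may impose because of an adverse event, so new events after that have no stated route into the 6-monthly SAE review

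*Protocol*

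**What the plan says.** Section 3.9 fixes both ends of the safety window. It opens at consent ("Collection of adverse events will commence from the time that the participant signs the consent to participate in the study") and closes as follows: "Routine collection of adverse events will continue until the participant completes the study or withdraws".

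Section 2.3 (Withdrawal criteria) gives three grounds on which the investigator may withdraw a patient: a diagnosed exclusion criterion, a protocol violation, and "Adverse or serious adverse events". None of them requires the patient to decline anything. The same section also says "The investigator will follow up any withdrawals", with no content or duration.

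Section 2.3 (Procedure to withdraw) adds two provisions. One is "Participants with clinically significant abnormalities requiring discontinuation will be followed until recovery from the abnormality, if possible". The other is that "an early termination visit will be encouraged with an attempt to collect the primary outcome". Discontinued participants may be replaced.

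Section 4 (Data Monitoring) appoints no monitoring committee. The investigating team discusses adverse events monthly. In addition, "The investigators will conduct a 6 monthly review of all SAEs", and the principal investigators stop the study if they judge the SAE rate too high. No numerical threshold is given.

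**The concern.** Worsening health can end safety observation. Adverse events are a withdrawal ground. Several exclusion criteria, if newly diagnosed, are also changes in health, such as diabetes or unstable hypertension or cardiac conditions. Once such a patient is withdrawn, routine collection stops, although the patient may be willing to stay in contact. The protocol does not separate stopping treatment, or leaving the visit schedule, from the end of safety data collection.

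Section 3.5 names serious possible effects of the very low energy diet: "In extreme cases vomiting, acute gout, acute gall bladder disease or cardiac disturbances". Suppose a patient is withdrawn in week 5 because of one of these and is admitted in week 8 with a different one. The first event is followed to recovery if possible. For the second, the protocol names nobody to ask about it, no time at which to ask, and no route by which it reaches the SAE review.

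That review carries weight because the investigators conduct it themselves, without an independent committee, in a trial of about 38 patients where a single SAE could affect their judgement. An analysis plan cannot repair the gap, since it cannot recover events that were never collected.

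**Working it through.** **Inputs**
- Completers required: 30. Dropout: about 20%. Number to randomise: 38 (section 4, Sample Size). Section 2.1 gives 30 as the number randomised; the section 4 figure is used here because it is the one that allows for dropout.
- Randomised phase: 3 months (section 3.1). Diet: the first 2 months of that phase (section 3.8, Dietary Component).
- Not in the protocol, so assumed: when withdrawals occur, that every planned dropout ends adverse event collection, and the SAE rate before and after withdrawal.

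**Reproducing the plan's figure**
- 30 / (1 − 0.20) = 37.5, rounded up to 38. This matches.
- Expected non-completers: 38 − 30 = 8, and 8/38 = 21%.

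**Patient-time without routine collection**

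Total randomised-phase time is 38 × 3 = 114 patient-months. If withdrawal occurs at month t, the time lost is 8 × (3 − t).

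| Withdrawal at | Patient-months lost | Share of 114 |
|---|---|---|
| 1 week (t = 0.25) | 8 × 2.75 = 22 | 19.3% |
| 1 month | 8 × 2 = 16 | 14.0% |
| 1.5 months | 8 × 1.5 = 12 | 10.5% |
| 2 months (end of diet) | 8 × 1 = 8 | 7.0% |

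**Share of SAEs missed, as an illustration**

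Take withdrawal at 1.5 months, a common SAE rate while under observation, and a rate k times as high after withdrawal. Observed time is 30 × 3 + 8 × 1.5 = 102 patient-months, and unobserved time is 12. The share missed is 12k / (102 + 12k).
- k = 1: 12/114 = 10.5%
- k = 2: 24/126 = 19.0%
- k = 5: 60/162 = 37.0%

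**Absolute scale**

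Twelve patient-months equal 12/3 = 4 patients observed for the full phase. If SAE risk were 1% to 10% per patient over 3 months (assumed) and unchanged by withdrawal, the expected number missed is 4 × 0.01 = 0.04 to 4 × 0.10 = 0.4.

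**Does another provision close the gap?**
- The general promise to follow up withdrawals has no content or duration, while section 3.9 states specifically that routine collection ends.
- Follow-up to recovery covers the abnormality that led to discontinuation, not new events.
- The early termination visit is encouraged rather than required, is a single contact, and has the primary outcome as its stated purpose.
- The monthly meetings can use only events that someone has recorded.

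**The case against.** The strongest reply is that the protocol does not abandon withdrawn patients. It promises to follow up all of them, follows the causal abnormality to recovery if possible, and tries to establish whether an adverse event lies behind a failure to return. Section 3.9 ends only routine collection. It ties an adverse event to the trial period, not to patients still enrolled, and requires all SAEs to be notified to the ethics committee. A later admission that came to light could therefore be recorded. This stands in part: it cannot be said that later events are lost, only that new ones have no stated means of being found and passed on.

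Four stronger readings are tempting, and the documents do not support them.
- **That the SAE rate is the only safety ground for stopping.** Section 4 bases stopping on safety data generally and has monthly discussion of all events, and section 2.3 allows discontinuation at any time on new safety information. The 6-monthly review is only the sole explicit SAE-rate review.
- **That the reviewed rate must be biased low.** Section 4 defines no denominator, and the analysis plan may. Per patient, missed events lower the rate. Per patient-month observed, they do so only if risk is higher after withdrawal.
- **That CPAP intolerance will unbalance observation between the arms.** Section 3.9 treats ceasing the device as a response to an adverse event, and section 4 keeps non-adherent patients in the analysis. A patient can stop CPAP and remain under collection.
- **That about 10% of safety information is lost to withdrawals caused by adverse events.** The figure counts all planned dropouts, including personal reasons and no-shows. The protocol gives no share due to adverse events.

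It is also fair to say that ending collection respects a patient's right to leave. That applies to patients who refuse contact, not to those whom the investigator withdraws.

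**Conclusion.** The point holds in a limited form. Section 3.9 sets a rule that ends routine adverse event collection at withdrawal, and withdrawal may itself follow from an adverse event. The follow-up in section 2.3 is either unspecified or confined to the causal abnormality. New events therefore have no stated route into the SAE review.

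The size is 7% to 19% of randomised-phase patient-time, and 10.5% if withdrawal averages 1.5 months. This assumes withdrawal between 1 week and 2 months and that all 8 planned dropouts end collection. If some stay in contact, the share is smaller. The expected number of missed SAEs is probably below one under the assumed risks, and with no stated threshold a changed stopping decision cannot be shown. It is a cheap improvement worth making, not a flaw that undermines the trial.

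**What to change.** Amend section 3.9 to separate withdrawal from treatment or visits from the end of safety collection:
- For every randomised patient who stops treatment or is withdrawn, for whatever reason, and has not refused further contact, collect adverse events and SAEs at least to the planned 3-month date, by phone where no visit takes place.
- Leave the existing collection period unchanged for patients who remain in the study. Appendix B places study completion at the 12-month visit, so the 3-month date must be worded as a minimum for withdrawn patients and not as a new end date for everyone.
- State that these events enter both the monthly discussion and the 6-monthly SAE review in section 4, and cross-refer to the follow-up promised in section 2.3.

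The cost is one or two sentences, consent wording for contact after withdrawal, and about 8 phone calls. Some patients will not be reachable, notably those who simply failed to return, so the gap will narrow but not close. The reported SAE rate may come out slightly higher. The change concerns data collection only and leaves treatment and clinical management as they are.

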#### ***4 Statistical Methods***

##### ***Sample Size:***

30 patients will be required to complete the randomised phase of this pilot study. Allowing for an approximate 20% dropout, n=38 will need to be randomised.

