## 2. Participants

### 2.1 Sample

**Sample size:** 30 patients randomised using a 1:1 ratio for VLED plus CPAP or VLED alone  
**Study Population:** Female and male adults with pre-diabetes and moderate-severe OSA recruited from obesity and sleep clinics and advertisements.

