## ***2.5 Recruitment Approaches***

### ***Hospitals:***

Approximately 30 participants will be entered in the pilot trial. Participants will be recruited via Woolcock, Royal Prince Alfred Hospital, University of Sydney, other affiliated sleep, endocrine and obesity physicians and advertisements.

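### Section 2.1 gives 30 patients as the number randomised, section 4 needs 30 to complete and 38 randomised, and an uncapped replacement rule leaves the final number open

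*Protocol*

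**What the plan says.** Section 2.1 (Sample) gives the sample size as "30 patients randomised using a 1:1 ratio for VLED plus CPAP or VLED alone". Section 2.5 (Recruitment Approaches, under Hospitals) says: "Approximately 30 participants will be entered in the pilot trial".

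Section 4 (Sample Size) attaches the figure of 30 to a different quantity: "30 patients will be required to complete the randomised phase of this pilot study". It continues: "Allowing for an approximate 20% dropout, n=38 will need to be randomised".

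Section 2.3 (Procedure to withdraw) adds a rule of its own: "Participants discontinuing from the study may be replaced", and then "A new randomisation number must be issued for the new participant". It sets no limit on replacements and does not mention the 20% in section 4.

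The Data Analysis paragraph of section 4 defines who is analysed: "Analysis will be by intention to treat and will include all participants who are randomised at 0 months".

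**The concern.** Thirty is the number randomised in section 2.1 and the number of completers in section 4. Both cannot hold once any dropout is expected, and nothing in the Protocol reconciles them. Staff working from section 2.1 would close recruitment at 30; staff working from section 4 would continue to 38. An ethics committee or a reader of the registered protocol cannot tell which number was intended, or later judge whether recruitment ended as planned.

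The replacement rule adds to this. Inflating for dropout and replacing dropouts both deal with the same loss, and the Protocol does not say whether they are alternatives or apply together. Because each replacement is a new randomisation, the total depends on how often a permissive rule is used.

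**Working it through.** **Inputs**

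- 30 completers required, about 20% dropout, 38 randomised: section 4, Sample Size.
- 30 randomised, 1:1: section 2.1.
- About 30 entered: section 2.5.
- Replacement allowed, new randomisation number, no cap: section 2.3.
- All randomised participants analysed: section 4, Data Analysis.

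**1. Reproduce the plan's figure.** Number randomised = completers / (1 − dropout) = 30 / (1 − 0.20) = 37.5, rounded up to 38. This matches section 4. (The common slip, 30 × 1.20 = 36, was not made.) In reverse, 38 × 0.80 = 30.4 expected completers.

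**2. Apply the same dropout to section 2.1.** 30 × 0.80 = 24 expected completers; 30 − 24 = 6 short. The two randomisation targets differ by 38 − 30 = 8 patients, and 8/38 = 21% of the section 4 figure.

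**3. Chance of reaching 30 completers.** Assume that each participant completes independently with probability 0.80 and nobody is replaced. With 30 randomised, all must complete: 0.80^30 = 0.0012. With 38 randomised, the binomial probability of at least 30 completers is 0.66.

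**4. What replacement does to the total.** Each replacement adds one to the number randomised. At exactly 20% dropout:

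- Start from 30 and replace until 30 complete: 30 / 0.80 = 37.5, about 38 randomised.
- Start from 38 and replace the expected dropouts once: 38 × 0.20 = 7.6; 38 + 7.6 = 45.6, about 46 randomised.

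The text permits either and chooses neither.

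**5. Illustrative precision.** The Protocol states no alpha, power, effect size or SD, so this is in SD units, for an unadjusted two-sample comparison of completers. The 95% CI half-width is t(0.975, 2n − 2) × √(2/n):

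- 15 per arm (30 completers): 0.748 SD.
- 12 per arm (24 completers): 0.847 SD.

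If one also assumes two-sided 5% alpha and 80% power (noncentral t), the detectable difference is 1.06 SD with 15 per arm and 1.20 SD with 12 per arm.

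**The case against.** The best defence is that section 4 is the statistical section, that it does set one number, and that its arithmetic is right. Section 2.5 is a soft figure in a recruitment paragraph and speaks of entry, not randomisation, so only section 2.1 contradicts section 4 outright. The replacement rule could also be how 30 enrolled becomes about 38 randomised, which is the first case in step 4 of the working. All of this is fair. The figure of 38 is not an error, and replacement need not be a second allowance on top of the first. But the Protocol does not state that reading, and section 2.1 still carries a wrong number under its sample-size label.

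A reader might infer more than the documents support:

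- *That a replaced dropout leaves the analysis.* The Data Analysis paragraph keeps everyone randomised. Section 2.3 encourages an early termination visit to try to obtain the primary outcome, and the replacement's new number leaves the dropout's own allocation in place.
- *That replacement biases the comparison because the trial is open label.* Under section 3.3 a newcomer receives the next number and a concealed assignment, from a list in random blocks of 2, 4 or 6 that enrolling staff cannot see. Replacement therefore cannot be steered to an arm. Section 4 plans no interim analyses. No bias in the estimate or the error rate is shown.
- *That about 48 would be randomised.* That is 38/0.80 = 47.5, which presumes a target of 38 completers. No section sets one.
- *That the trial loses stated power.* It is a pilot that claims none. The planned analysis is a repeated-measures mixed model over all randomised participants, so the SD-unit figures only show scale.

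**Conclusion.** The point stands as a contradiction in the enrolment target, with an unlinked replacement rule beside it. Section 2.1 conflicts directly with section 4, by 8 patients; section 2.5 is a looser echo of section 2.1. Following section 2.1 would miss section 4's own completer requirement by about 6, if dropout is the 20% the plan expects and nobody is replaced. On the illustrative scale, that widens a completers' 95% CI half-width from about 0.75 to 0.85 SD. Section 2.3 separately leaves the final number randomised without an upper limit. The defect is an ambiguous target. It is not a faulty calculation, an unsound analysis set or a demonstrated bias.

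**What to change.** In sections 2.1 and 2.5, replace 30 with 38 randomised 1:1, about 30 of whom are expected to complete. Section 4 can stay as it is. Do not promise 19 per arm: with random blocks of 2, 4 or 6, a total of 38 can end as 20 and 18.

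In section 2.3, do one of two things. Either delete the replacement sentence, or keep it and state that 38 already includes the dropout allowance and is the maximum number randomised. With either option, add that every randomised participant, whether a dropout or a replacement, stays in the intention-to-treat analysis defined in section 4.

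The cost is a text correction in three sections, using a number the Protocol has already derived. No treatment, assessment or analysis method changes.
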